## Brief Summary/Abstract

The rapidity with which progesterone suppresses daytime LH (and by inference GnRH) pulse frequency is unknown. We propose to assess this further using a randomized, cross-over, placebo-controlled study. Normally-cycling women and women with PCOS (both pretreated with estradiol) will undergo a 24-h sampling study. After 10 h of sampling, either oral micronized progesterone (100 mg p.o.) suspension or placebo suspension will be administered (according to randomization). During a subsequent menstrual cycle, subjects will undergo another study identical to the first (including pretreatment with estradiol) except that oral progesterone will be exchanged for placebo or *vice versa* in accordance with the crossover design. We will assess the acute effects of progesterone on LH frequency, with secondary endpoints being mean LH, LH pulse amplitude, and mean FSH. We hypothesize that (1) administration of progesterone (at 0600 h) to adult women during the follicular phase will result in a demonstrable suppression of daytime LH (and by inference GnRH) pulse frequency within 12 hours; and (2) administration of progesterone (at 0600 h) to women with PCOS (during the follicular phase) will result in less suppression of daytime LH pulse frequency than in controls.

## Background

### 1. Provide the scientific background, rationale and relevance of this project.

It remains unknown how rapidly progesterone (P) affects gonadotropin releasing hormone (GnRH) pulse frequency slowing in normal women or in women with PCOS. Through this study, we are pursuing this question to confirm an important assumption in our overall hypothesis regarding how cyclic ovulation is established during puberty.

GnRH stimulates LH and FSH synthesis and secretion from the same gonadotrope cell; nonetheless, LH and FSH levels change differentially throughout ovulatory cycles, with FSH predominance in the early follicular phase and LH predominance in the late follicular phase (1-7). These variations in gonadotropin secretion result in part from different patterns of pulsatile GnRH stimulation, with fast GnRH pulse frequencies favoring LH and slow GnRH pulse frequencies favoring FSH synthesis and secretion (8-12).

In ovulatory women, LH (and by inference GnRH) pulse frequency slows from one pulse every 60-90 min in the follicular phase to approximately one pulse every 4-6 h during the luteal phase. Luteal slowing of GnRH pulse frequency increases FSH synthesis, but high luteal levels of estradiol (E2) and inhibin prevent FSH release from the gonadotrope (13, 14); when E2 and inhibin concentrations fall during the luteal-follicular transition (i.e., when inhibition of FSH secretion is removed), an increasing GnRH pulse frequency leads to the early follicular monotropic rise of FSH. Thus, the ability to slow GnRH pulse frequency during the luteal phase appears to be important for the early follicular rise in plasma FSH and, therefore, follicular development.

Progesterone appears to be the primary effector of GnRH pulse frequency slowing. GnRH pulse frequency slows coincident with P increases in the luteal phase, and administration of P to women during the follicular phase also slows GnRH pulse frequency (15), although the rapidity with which this occurs is unknown. Progesterone's ability to slow GnRH pulse frequency appears to require the permissive presence of E2 (16, 17), possibly reflecting E2's ability to induce hypothalamic P receptors (18-21).

Changes of GnRH pulse frequency are also seen during puberty. During childhood, the hypothalamic-pituitary-gonadal axis is quiescent with low plasma LH and FSH levels, low LH pulse amplitude, and slow LH (GnRH) pulse frequency (i.e., detectable pulses approximately every 3-6 h), and high FSH:LH ratio (22-26). Reactivation of this axis at puberty is heralded by sleep-entrained

IRB-HSR# 13368: Determining the rapidity with which exogenous P suppresses daytime LH (GnRH) pulse frequency in women during the follicular phase of the menstrual cycle (CRM001)

amplification of LH (GnRH) pulsatility, with nocturnal increases in both LH pulse amplitude and frequency (23, 24, 27-34). The cause(s) of these diurnal changes in GnRH pulsatility is(are) unclear, but diurnal changes of sex-steroids, which also occur during this time, likely play a major role. Overnight increases of testosterone (T) (35-38) and E2 (25, 39, 40) occur in pubertal boys and girls, respectively. E2 infusion in peripubertal girls (41), in addition to infusions of either T (42, 43) or E2 (33) in peripubertal boys, mitigates nocturnal increases in LH pulsatility. Moreover, in contrast to diurnal changes of LH and E2 in normal pubertal girls, age-matched girls with gonadal dysgenesis exhibit elevated LH pulse frequencies at all time periods (34, 44). Thus, diurnal changes in sex-steroids appear to direct diurnal changes in GnRH pulse frequency.

Since P is the primary effector of GnRH pulse frequency slowing in adult women, and with data that suggests that P increases 2.3-fold overnight in early pubertal girls (45), *we believe that P may be the major effector of diurnal GnRH pulse frequency slowing in peripubertal girls.*

It is unclear what functional significance underlies these diurnal variations in GnRH pulsatility during puberty; however, by analogy to adult women, we suggest that diurnal slowing during puberty may be important for enhancement of FSH synthesis and corresponding follicular development.

Original hypothesis regarding the development of ovulatory cycles in peripubertal girls: We initially proposed that in normal pubertal adolescent girls, sleep-entrained increases of LH pulsatility drive production of sex steroids (P and E2), which in turn suppress pulsatile GnRH (LH) secretion during the subsequent day. (Progesterone production may also be of adrenal origin under diurnal ACTH control.) These diurnal decreases in GnRH pulse frequency enhance FSH production and are therefore important for follicular development. Increasing FSH production results in escalating waves of follicular development and corresponding increases in E2 production. Estradiol concentrations eventually become adequate to trigger an LH surge, and the (ovulatory) follicular remnant is transformed into a corpus luteum that secretes great quantities of P and E2; thus occurs the first luteal phase. Later anovulatory cycles are associated with small increases in P, which appear to be adequate to reduce GnRH pulse frequency in normal women (46).

These processes have major implications for normal pubertal development and for aberrations of this process that appear to occur in adolescents destined to develop PCOS. Hyperandrogenism during adolescence, felt to represent a forerunner of PCOS, is associated with disordered LH secretion. Results from our group (IRB-HSR# 8588, JCM010) suggest that the GnRH pulse generator is relatively resistant to the feedback actions of P and E2 in some hyperandrogenemic adolescents (47), similar to that described in women with PCOS (48, 49). If this is indeed the case, then the aforementioned sequence of events at puberty would be quite different in hyperandrogenemic adolescents. As puberty begins, nocturnal increases of LH (and possibly ACTH) pulsatility would drive production of P and E2. However, these relatively low sex steroid concentrations would be insufficient to overcome GnRH pulse generator resistance, and a relatively rapid GnRH pulse frequency would persist throughout the following day. Persistently rapid GnRH pulses would be expected to result in both LH excess, which would stimulate excessive androgen production, and relative FSH deficiency, which would hinder normal follicular development. These hypotheses are consistent with available data.

In a recent study of 8 normally cycling women (nearly identical to the current study), we administered a single dose of P at 1800 h and monitored changes (before vs. after P) of LH pulse characteristics. Each subject also underwent a GCRC admission where placebo (PBO) was administered at 1800 h. A manuscript describing our findings has been published (50). The 10-hour mean P concentration increased from  $0.6 \pm 0.1$  ng/ml before P (0800-1800 h) to  $3.9 \pm 0.3$  ng/ml after P administration (2200-0800 h;  $P < 0.01$ ). LH pulse frequency (based on both [a] LH pulse counts over 10 hours and [b] ten-hour mean LH interpulse intervals) decreased significantly after both P and placebo administration, with no significant difference between P and placebo (Figure 1, next page). In contrast, mean LH, LH amplitude, and mean FSH increased significantly within 4 hours of P administration, but not after placebo.

We concluded that in  $E_2$ -pretreated women in the late follicular phase, (1) *nocturnal* LH pulse frequency is not acutely (within 12 hours) influenced by P administration; (2) an acute increase in P causes pronounced augmentation of gonadotropin pulse amplitude within 4 hours; and (3) LH pulse frequency slows overnight during the second half of the follicular phase.

The absence of P-induced slowing of LH frequency is in contrast to animal studies that suggest a rapid (within 2-6 hours) decrease in LH and GnRH pulse frequency after P administration. For instance, in ovariectomized but  $E_2$ -replete ewes, P dramatically suppresses GnRH pulse frequency over 12 h; this

IRB-HSR# 13368: Determining the rapidity with which exogenous P suppresses daytime LH (GnRH) pulse frequency in women during the follicular phase of the menstrual cycle (CRM001)

effect appears to begin within 2 h and is blocked by the progesterone-receptor antagonist mifepristone (RU-486) (51). Similarly, in bovine females, changes in LH pulse frequency are observed within 6 h of altered P concentrations (52). Although species differences may account for this discordance, we have considered an alternative explanation.

Nocturnal, sleep-related slowing of LH pulse frequency during the early follicular phase is well described. Our data (above) and several studies by Loucks and colleagues (53-55) suggest that late follicular LH pulse frequency also slows by 20-30% during sleep. Nocturnal slowing of LH frequency in the early follicular phase (and presumably in the late follicular phase) appears to be specifically related to sleep and is likely driven by higher CNS systems.

These nocturnal changes in LH pulse frequency are interesting in light of what is observed during puberty. In early pubertal girls (and boys), nocturnal LH frequency *increases* compared to daytime LH frequency. It is generally believed that the overnight increase of LH pulsatility during puberty is driven by higher CNS systems.

Of particular interest, our preliminary data in peripubertal girls suggests that nocturnal LH frequencies in early pubertal girls, late pubertal girls, and the 8 adult women studied under JCM016 are very similar, while late evening LH frequencies (i.e., from 1900-2300 h – a surrogate for daytime frequency) are varied (Figure 2). These data are consistent with the notion that higher CNS systems may in large part determine nocturnal GnRH pulse frequency during puberty and in adults. Accordingly, sleep-associated (and presumably CNS-driven) LH frequency may be similar in pubertal girls and adult women, with daytime frequencies being controlled by other factors.

In addition, two of the aforementioned studies by Loucks and colleagues reported that dietary restriction slows daytime—but not nighttime—LH pulse frequency in the late follicular phase (53, 55). This suggests that daytime and nighttime LH frequency may be differentially affected by experimental maneuvers.

On the basis of the above observations, we have considered the possibility that *daytime* (or non-sleep-associated) LH frequency is acutely responsive to changes in P concentrations in women, even though nighttime frequency is not. This would be consistent with the notion that CNS control of *nocturnal* LH frequency may override hormonal control, at least in the short-term. We would like to test this hypothesis by using a protocol identical to the earlier JCM016 protocol except that the timing of the sampling and P (and PBO) administration is altered by exactly 12 hours (e.g., P and PBO are administered at 0600 h instead of 1800 h).

We will also study women with PCOS in this protocol, primarily to assess for potential abnormalities of acute negative feedback by P (i.e., the rapidity with which P slows LH pulse frequency). But as a secondary aim, we will also assess for abnormalities of *positive* feedback (i.e., P-induced increases of LH amplitude and mean LH).

[figure not shown]

Figure 2. LH pulse count over 4-h time blocks in normal Tanner 1-3 girls (open circles; n = 7), normal Tanner 4-5 girls (closed circles; n = 9), and normal adult women who were studied in the late follicular phase under the JCM016 protocol (squares; n = 8).

## IRB-HSR# 13368: Determining the rapidity with which exogenous P suppresses daytime LH (GnRH) pulse frequency in women during the follicular phase of the menstrual cycle (CRM001)

As mentioned above, studies demonstrate that the GnRH pulse generator is relatively resistant to the negative feedback effects of longer-term administration of P in adults with PCOS (48, 49). In women taking combined oral contraceptives, LH (GnRH) pulse frequency is increased in PCOS compared to controls (49). Similarly, in a study where 7 days of exogenous P and E2 were given (to achieve physiologic concentrations) to women with PCOS and controls, LH pulse frequency was suppressed by 60% in controls, but by only 25% in PCOS (48). Similar findings are observed prenatally-androgenized sheep (56), an animal model of PCOS. In adult PCOS, this relative resistance of the GnRH pulse generator to P negative feedback appears to be mediated by T excess, as it is reversed by the androgen-receptor blocker flutamide (57). Mouse studies also reveal that DHT impairs the ability of P to slow GnRH firing rate (58). This effect of androgens may reflect reduced basal and E-induced P receptors in the hypothalamus (59). Thus, we expect that P will be less effective (in reducing LH frequency) in PCOS compared to controls.

We are unaware of any studies investigating the *positive* feedback effects of P in PCOS, a potentially important factor contributing to ovulatory dysfunction. As described above, our earlier study (50) disclosed a rapid (within 4 h) and pronounced augmentation of gonadotropin secretion after oral P administration in E2-pretreated women. Similar findings have been described previously (60-62). These effects of P on gonadotropin secretion appear to be related, at least in part, to augmentation of GnRH-stimulated release of gonadotropins from pituitary gonadotropes (62, 63). On the basis of these data, it is generally held that the late follicular rise in P—which begins ~12 h before the LH surge (61, 64)—is an important mechanism contributing to the midcycle LH surge. However, relative resistance to the *positive* feedback effects of P could represent another mechanism by which ovulatory function is reduced in PCOS. That is, we hypothesize that LH amplitude and mean LH will not increase after P administration to the degree observed in controls.

### Hypothesis to be Tested

We propose two primary hypotheses: (1) administration of progesterone (at 0600 h) to normally cycling adult women during the follicular phase will result in a demonstrable suppression of daytime LH (and by inference GnRH) pulse frequency within 12 hours; (2) administration of progesterone (at 0600 h) to women with PCOS (during the follicular phase) will result in less suppression of daytime LH pulse frequency than in ovulatory women without PCOS. We will also assess the acute effects of progesterone on mean LH, LH pulse amplitude, and mean FSH. A secondary hypothesis is that LH augmentation after progesterone administration will be less in PCOS compared to normal controls.

### Study Design: Biomedical

#### 1. Will controls be used? Yes

##### ► IF YES, explain the kind of controls to be used.

This is a cross-over study; thus, when evaluating the effects of progesterone vs. placebo, subjects will serve as their own controls. Also, the data from women with PCOS will be compared to data in normal women (controls).

#### 2. What is the study design?

Double blind until data analysis (progesterone concentrations are measured, which will disclose whether progesterone or placebo was given).

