**4. How many subjects will sign a consent form under this UVa protocol?**

90 subjects will sign a consent form under this protocol. (*Notably, we will stop recruiting when we have obtained complete and interpretable data for 12 women with PCOS and 12 controls*). (Update at time of 5-year renewal April 2017: we have completed study of all required controls, and we are nearing completion of study in women with PCOS.)

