**3. Provide a justification for the sample size used in this protocol.**

Sample size/statistical power: The primary endpoint will be the change in LH pulse frequency (over 10 h) attributable to P. The null hypothesis is that 10-h (1000-2000 h) LH frequency after P administration will be the same as 10-h (1000-2000 h) LH frequency after placebo administration. Estimates of within-subject variability utilized in the calculation (column 2 of table below) were based on our preliminary data. Assuming that 12 women in both groups complete both CRU admissions (placebo admit, P admit), we list in column 3 (table) the estimates for the minimum detectable absolute difference between the mean change in 10-h LH pulse frequency that would provide ≥ 80% statistical power.

Endpoint	Within-subject standard deviation	Minimum detectable P effect on LH frequency
Change in LH pulse-interval (min)	20.6	16.7
Change in # of LH pulses / 10-h	1.24	1.0

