After 3 d of E2 administration, women will undergo a 24-h sampling study in the CRU, alternate UVA hospital unit, or off-site hotel. Estradiol administration (E2 patches) will continue throughout the overnight admission. Subjects will be admitted to the CRU, alternate UVA hospital unit, or hotel at 1800 h (2 h prior to sampling). Beginning at 2000 h, blood will be obtained through an indwelling i.v. forearm heparin lock over a 24-h period as follows: LH every 10 min (1 ml); P every 30 min (1 ml); FSH, E2, and T every 2 h (assays to be run in same samples as LH and P). SHBG, fasting insulin, and fasting glucose (i.e., fasting since 2200 h) will be run on the 0600 h sample (extra 2 cc drawn). (Subjects will fast from 2200 to 0600 h.) After 10 h of sampling (i.e., at 0600 h), either oral micronized P (100 mg p.o.) suspension or placebo suspension will be administered (according to randomization). (NOTE: the study coordinator will pick up the P/placebo from the research pharmacy to send to the CRU, alternate UVA hospital unit, or hotel the evening before administration.) With exogenous P, we aim to achieve mean plasma P concentrations 4-8 ng/ml. Subjects will not be allowed to sleep during the day (i.e., from 0600 to 2200 h). Subjects will be encouraged to sleep from 2200 to 0600. When possible, sleep will be formally evaluated (extraoculograms, electroencephalograms, wrist actigraphy, etc.)footnote  
. At the completion of sampling, E2 patches will be discontinued. Volunteers will be discharged on oral iron (325 mg BID). We will ask women to eat only the food provided by the CRU staff.

Subjects will undergo another overnight study identical to the first (including pretreatment with E2, outpatient blood draw 4-5 days before admission, etc.), except that oral P will be exchanged for placebo or *vice versa* in accordance with the crossover design. (Subjects will again begin E2 patches on the evening of cycle day 4-8 [controls] or  $\geq 4$  days post-menses [PCOS].) In this way, we will be able to standardize any change in GnRH pulse frequency after P administration to any change in GnRH pulse frequency after placebo administration.

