ADDITIONAL NOTE: As this is a study to determine the effects of acute progesterone administration on LH hormone regulation, it is important to study subjects during the follicular phase (a time when progesterone should be low, < 1.0), rather than during the luteal phase (when progesterone is high). For ovulatory control subjects, the timing of the luteal phase is predictable, so admission usually occurs around menstrual cycle day 7-11 (during the follicular phase). However, subjects with polycystic ovary syndrome have infrequent/irregular ovulation and infrequent/irregular luteal phases, so it is harder to predict when they will be in the luteal phase. For this reason, overnight admission is scheduled at a time that is  $\geq 7$  days since their last menses began; and a progesterone level is checked within 1-5 days before the overnight admission, to help rule out the possibility that women will be studied during the luteal phase (i.e., when progesterone levels are high). Following completion of the second overnight admission, samples will be assayed in the Center for Research in Reproduction Ligand Assay Core Lab for progesterone and LH. If it is found that a subject had a high progesterone level (> 1.0 ng/mL) prior to administration of progesterone/placebo syrup at 6am during either of their study admissions, the subject will be asked to repeat that particular study admission at a time when they are in the follicular phase of their cycle (progesterone < 1.0 ng/mL). The subject would be asked to wait the appropriate 8 weeks before scheduling the repeat study admission, so as not to put the subject at undue risk for anemia. The exact timing of the repeat study admission will depend on the subject's menstrual cycle. We would obtain all of the appropriate safety labs prior to studying the subject for a final study admission (to ensure subject safety). And to prevent a repeat occurrence of catching the subject in the wrong phase of her cycle, a progesterone would be checked one to two days before admission. Importantly, in such a situation, subjects would not be obligated to repeat the study admission, and they would receive \$300 for completing the study even if they do not repeat the admission. However, if they indeed complete the extra admission, we would offer additional compensation of \$100 for completion of this extra study admission, consistent with compensation for each overnight admission under this protocol.

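### The blind lasts only until data analysis, and nothing requires LH pulses, the basis of the primary endpoint, to be identified and locked before progesterone results reveal treatment

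*Combined protocol and SAP*

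**What the plan says.** Study Design: Biomedical, item 2, sets the duration of the blind: "Double blind until data analysis (progesterone concentrations are measured, which will disclose whether progesterone or placebo was given".

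Statistical Considerations, item 3, defines the endpoint: "The primary endpoint will be the change in LH pulse frequency (over 10 h) attributable to P". Its table row "Change in # of LH pulses / 10-h" gives a within-subject SD of 1.24 and a minimum detectable effect of 1.0 pulse. Items 4 and 5 there describe mixed-effects ANOVA models for pulse frequency and the secondary outcomes. None of these items names a pulse-detection method, a threshold, a masked reader, or a point at which pulse calls are locked.

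Biomedical Research, item 1, gives the sampling scheme, "LH every 10 min (1 ml); P every 30 min (1 ml", and the level aimed for after active drug: "With exogenous P, we aim to achieve mean plasma P concentrations 4-8 ng/ml". Its additional note describes the follicular phase as "a time when progesterone should be low, < 1.0". The same note says that after the second admission "samples will be assayed in the Center for Research in Reproduction Ligand Assay Core Lab for progesterone and LH". A progesterone value above 1.0 ng/mL before the 0600 h dose leads to a request to repeat that admission.

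Human Participants, item 4, adds that "we will stop recruiting when we have obtained complete and interpretable data for 12 women with PCOS and 12 controls". What makes an LH profile interpretable is not defined.

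**The concern.** No assay reports a pulse count. The count is derived from the LH series, and that derivation could fall on either side of the moment at which treatment becomes known. Progesterone is measured in the same 24-hour sampling as LH and assayed in the same core laboratory. The target range after active drug (4-8 ng/ml) does not overlap the expected follicular level (below 1.0), so anyone who sees the post-dose progesterone series can tell which admission was which.

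At stake is the contrast that the trial is built on. If borderline rises are judged, or detection settings chosen, with treatment visible, any systematic tendency enters the progesterone-minus-placebo difference. The placebo admission does not remove it, because such a tendency is by its nature different for the two treatments. The investigators also state a directional hypothesis, that progesterone suppresses frequency.

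**Working it through.** **1. Order of events.** I set the relevant sections side by side.

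- Study Design, item 2: the blind ends at data analysis, because progesterone results disclose treatment.
- Biomedical Research, item 1: LH and progesterone are both assayed after each woman's second admission, and pre-dose progesterone is then used to decide on a repeat admission. Who sees the results is not stated.
- Statistical Considerations, item 4: the analysis plan takes 10-h pulse frequency as its input. How and when the counts were produced is not stated.
- Data and Safety Monitoring Plan, 2.5: the only listed criterion for breaking the blind is a severe adverse event within 24 hours of dosing.

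No section places pulse identification before disclosure, and no section places it after.

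**2. The plan's own figures.** Inputs: SD 1.24 pulses or 20.6 min, n = 12, power 80% (item 3). Two-sided alpha of 0.05 is my assumption, since item 3 gives none and item 4 mentions only a 95% confidence interval.

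Minimum detectable effect = (1.960 + 0.842) × SD / √12

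- Pulses: 2.802 × 1.24 / 3.464 = 1.003, stated as 1.0.
- Interval: 2.802 × 20.6 / 3.464 = 16.66 min, stated as 16.7.

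Both reproduce, treating the SD as that of the paired difference.

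**3. Scale of one call.** The Background gives one follicular-phase pulse every 60-90 min, so 600 min holds 600/90 = 6.7 to 600/60 = 10 pulses. The detectable effect is 1.0 pulse. A net shift averaging a full pulse across women would equal all of it, and smaller shifts are fractions of it.

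**4. Illustration of a shift.** Suppose the true effect is zero and calling moves the mean progesterone-minus-placebo difference by b pulses. The test is a paired t with 11 df and critical value 2.201. The rejection probability comes from the noncentral t with noncentrality b/SE.

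- If 1.24 is the SD of the paired difference: SE = 1.24/√12 = 0.358.
- If 1.24 is a per-admission SD: SE = 1.24 × √2/√12 = 0.506.

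| Assumed shift b | Noncentrality, SE 0.358 | False-positive rate | Noncentrality, SE 0.506 | False-positive rate |
|---|---|---|---|---|
| 0 | 0 | 5% | 0 | 5% |
| 0.25 | 0.70 | 9.8% | 0.49 | 7.4% |
| 0.50 | 1.40 | 24.8% | 0.99 | 14.7% |

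The shift sizes are assumed. The documents contain nothing from which to estimate them.

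**5. Which hypothesis is affected.** Let the shift be b_C in controls and b_P in PCOS. The progesterone-versus-placebo estimate in controls (hypothesis 1) is biased by b_C. The PCOS-versus-control difference in that effect (hypothesis 2) is biased by b_P − b_C, which is zero when the two are equal.

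**The case against.** The strongest reply is that the plan never says pulses are called unblinded. A reader might infer from Study Design, item 2, that the blind ends before pulses are identified. The text does not support that: the data analysis plan in Statistical Considerations, item 4, starts from pulse frequency, so the phrase can equally mean modelling counts already in hand. This stands, and the point is confined to an order that is left open.

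Second, if a fixed algorithm with preset settings is used, knowing the treatment cannot move a count. This also stands, but no such algorithm is written down. It is a reason to name one.

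Third, calls that vary without regard to treatment add noise and not bias, and a shift of equal size in both groups cancels in the PCOS comparison. Both are correct, and both limit the reach of the concern.

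Fourth, coding may not mask treatment fully. The Background reports that in the nearly identical earlier study LH amplitude rose within 4 hours of progesterone but not after placebo, so a coded profile may still hint at treatment. This stands, and the remedy therefore needs fixed settings as well as coding.

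Fifth, the wording about interpretable data is a recruitment target and not an exclusion rule, and the repeat-admission criterion that is written down is numeric and pre-dose. A reader might infer that profiles will be dropped with treatment visible. The documents do not say so. They leave the term undefined for LH profiles and do not say when it is judged.

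**Conclusion.** The concern holds in a limited form. The stated duration of the blind does not protect the step that creates the primary endpoint, because no rule requires pulse calls to be complete before disclosing results are seen. Whether calls are in fact made with treatment known, and whether they involve judgement, cannot be determined from the documents.

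If both are so, the progesterone-versus-placebo estimate is exposed directly, and the PCOS-versus-control comparison only to the extent that the shift differs between groups. The false-positive rates of about 10-25% or 7-15% should not be read as an estimate of what will happen. They rest on an assumed shift of 0.25-0.5 pulse, a two-sided alpha of 0.05, n = 12, and one or the other reading of the SD of 1.24. They show only that a fraction of a pulse matters when the detectable effect is one pulse.

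The plan should be changed, because the protection is cheap and it bears on the primary contrast.

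**What to change.** In Study Design: Biomedical, item 2, replace the current rule with: *Double blind until the LH pulse data set is locked.* Then add to Statistical Considerations, item 4:

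- Name the pulse-detection method and its settings in advance, and apply them identically to every LH series.
- Have the laboratory release LH series under a code.
- Complete and lock all pulse calls, and any decision that a profile is not interpretable, before treatment codes or progesterone results from after 0600 h reach anyone who handles the LH series.
- Before the lock, release only pre-dose progesterone. The repeat-admission check in Biomedical Research, item 1, needs nothing more.

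This needs no new samples or participants and no change in sample size. For future series it is only an order of release. Because the April 2017 update reports the controls complete and PCOS nearly so, any series already called with treatment known must be re-run under code with the fixed settings. That is a small amount of rework.
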